## 4. STUDY ELIGIBILITY

### 4.1 Inclusion Criteria

To be enrolled in this study, subjects must meet all of the following criteria:

1. 45-85 years of age (inclusive) within 30 days of enrollment (target  $\geq 70\%$  of subjects to be 65-85)
2. Willing to undergo a SOC screening CS within 90 days of blood collection
3. Considered by a physician or healthcare provider to be “average risk” for CRC
4. Able and willing to provide blood samples per protocol
5. Able to comprehend and willing to sign and date the informed consent document(s)

### 4.2 Exclusion Criteria

Subjects will be excluded from enrolling into the study if any of the following are met:

1. Family history
  - 1.1. At least 1 first-degree relative diagnosed with CRC before the age of 60 (Note: First-degree relatives include parents, siblings and offspring.)
  - 1.2. At least 2 first-degree relatives diagnosed with CRC at any age

1.3. Known hereditary gastrointestinal cancer syndrome including but not limited to the following:

- 1.3.1. Hereditary non-polyposis CRC syndrome (HNPCC) or Lynch Syndrome
- 1.3.2. Familial adenomatous polyposis (FAP)
- 1.3.3. Cowden's Syndrome
- 1.3.4. Juvenile Polyposis Syndrome
- 1.3.5. MUTYH-associated Polyposis
- 1.3.6. Peutz-Jeghers Syndrome
- 1.3.7. Serrated Polyposis Syndrome

2. Personal history

- 2.1. CRC or colorectal adenoma
- 2.2. History of any malignancy (except for non-melanoma skin cancer) at the time of enrollment, and for the 5 years preceding enrollment
- 2.3. Inflammatory bowel disease (IBD), including chronic ulcerative colitis (CUC) and Crohn's disease (CD)
- 2.4. Total colonic resection
- 2.5. Cystic fibrosis (CF)
- 2.6. CS in the 9 years preceding enrollment with the exception of an incomplete colonoscopy, or for a poor or inadequate bowel prep
- 2.7. Sigmoidoscopy or CT colonography in the 4 years preceding enrollment
- 2.8. Stool DNA testing in the 2 years preceding enrollment
- 2.9. Fecal occult blood testing (FOBT) or fecal immunochemical testing (FIT) in the 6 months preceding enrollment
- 2.10. Requiring an immediate or emergent colonoscopy for the investigation of symptoms
- 2.11. Solid organ or bone marrow transplantation
- 2.12. Blood product transfusion in the 120 days preceding enrollment

2.13. Any trauma or surgery requiring overnight inpatient hospitalization in the 30 days preceding enrollment

3. A medical condition which, in the opinion of the Investigator, should preclude enrollment in the study
4. Participated in or currently participating in a clinical research study in which an experimental medication has been administered during the 60 days up to and including the date of providing informed consent or may be administered through the time of the CS
5. Known to be pregnant

## 5. STUDY PROCEDURES

### 5.1 Informed Consent and Enrollment

Subjects must be able to provide informed consent prior to any study procedure. Subjects who provide informed consent, meet the eligibility criteria and provide the blood sample for this study will be enrolled.

### 5.2 Colonoscopy, Histopathology, and Imaging Reports

Each subject will undergo a SOC screening CS within 90 days of blood collection. Bowel preparation and CS will be performed according to SOC at each site. The endoscopist will record the quality of the bowel preparation after washing and suctioning. A CS that was limited in any way but wherein a CRC was identified or wherein a partially obstructing CRC was identified, will be included in the analyses.

For all non-CRC subjects, the following will apply:

A subject who has a bowel preparation rated as less than fair (i.e., poor or inadequate) will be considered unevaluable and therefore excluded from analysis of all primary and secondary endpoints. (Poor is defined as semisolid stool that could not be suctioned or washed away, and < 90% of mucosa is seen; inadequate is defined as needing repeat preparation or screening.)

A subject who has an incomplete CS will be considered unevaluable and therefore excluded from analysis of all primary and secondary endpoints. (A complete CS will be defined as reaching the cecum; reaching the junction between the small and large intestine if the cecum has been resected; or reaching the neo-cecum. Cecal intubation will be documented by photographic evidence and/or documentation of cecal intubation.)

A non-CRC subject who has (1) a poor or inadequate bowel preparation or (2) an incomplete CS may repeat the CS and continue as a subject for this study only if the repeat CS occurs within 90 days of the blood collection.

CS findings will be recorded on the CS reports in accordance with the standard of practice at each site. Histopathological results will also be conducted according to usual practice at each site. Results from the CS and, if performed, histopathology will be recorded in the clinical database. All results (e.g., CS, histopathology, and imaging reports) will be collected, de-identified, labeled with the subject ID and uploaded to a clinical study database. Personnel generating any of these clinical reports will remain blinded to the results of Freenome's test, and vice versa.

The following required information will be collected once available:

- CS report
- If applicable, any histopathology report(s)
- If applicable, any imaging reports or relevant histopathology or operative notes required for cancer staging

### **5.3 Central Pathology**

Each patient will have their respective CS report and (if applicable) local histopathology report reviewed by a central pathologist in order to categorize the index lesion (if applicable) into the histopathological categories described below in section 7.2 (i.e., CRC, AA, NAA, and NEG). For all cases categorized as AA2.1, AA2.2, AA2.4, and AA2.5 and for 5% of NEG4.1, central pathology review will be required. The sites will send H&E slides, formalin-fixed paraffin embedded (FFPE) blocks or digital images for review of these specific cases. When the classification of the index lesion differs between the local histopathology result and the central pathology result, the case will undergo review by an additional central pathologist to adjudicate the final categorization of the index lesion. Instructions will be included in the central pathology manual.

H&E slides, FFPE blocks or digital images of the selected cases will be sent for central pathology review as detailed above. (H&E slides are preferred.) After analysis of the H&E slides or H&E slides made from FFPE blocks, slides and/or blocks will be returned to sites. Digital images will be stored in a secure site.

### **5.4 Data Collection**

Refer to Section 3.5. Schedule of Assessments. The following information will be recorded in the electronic case report form (eCRF) for each subject after consent at enrollment.

- Medical History / Demographics
- Concomitant medications (specifically aspirin, estrogen, disease-modifying anti-rheumatic drugs (DMARDs), biological agents, and COVID-19 vaccinations) in the 30 days preceding enrollment, as listed in [Appendix I](#)
- Lifestyle information will be obtained either from the subject's clinical record or self-report, including but not limited to:
  - History of tobacco product use (i.e., cigarettes)
  - History of and current information on alcohol consumption and drugs of abuse including recreational and prescribed, including tetrahydrocannabinol (THC)
- Blood collection time and date
- Height and weight

## 5.5 Blood Specimen Collection and Storage

Blood specimens collected for this study will be separate from any specimens collected for SOC. Up to 50 mL of peripheral blood will be collected prior to the bowel preparation via standard phlebotomy. Subjects will have the option to have blood collected either at the study site or via mobile phlebotomy services, in which case the subject can have blood collected in their home or location of preference. The blood collection tubes will be labeled using supplied barcode labels which link to the unique study subject ID, as described in the study laboratory manual.

Refer to the study laboratory manual for complete instructions on blood collection procedures, labeling, handling, storage, and shipment.

Residual blood samples may be destroyed or, if the subject consents, archived for further research. Clinical data and samples will be kept in a manner that preserves the anonymity of subjects, using the subject ID as the only tracking information. Specimens will be stored for no more than 20 years in Freenome's biorepository or a similar commercial biorepository contracted by Freenome, and may be used for future research, which may improve the researchers' understanding of cancer or other diseases.

## 6. ADVERSE EVENTS

### 6.1 Adverse Event (AE) Definition

Due to the study design and the nature of the blood collection process, the Sponsor does not expect many adverse events (AEs) caused by or related to the blood collection.

Since the screening CS is being performed as SOC and is a routine part of patient care, subjects are at no increased risk because of participation in this study. Thus, while adverse events may be anticipated due to SOC screening CS, they are not regarded as study related.

For the purposes of this study, an AE is defined as any undesirable physical, psychological or behavioral effect experienced during participation in the study that is related to the blood collection for this study. As a result of blood collection, subjects may experience minor pain, discomfort, bruising at the venipuncture site, or lightheadedness.

### 6.2 Serious Adverse Event (SAE) Definition

A serious adverse event (SAE) is any AE that meets any of the following criteria:

- Death
- A life-threatening illness or injury
- Medical or surgical intervention to prevent permanent impairment of a body structure or body function
- Required inpatient hospitalization or prolongation of existing hospitalization
- Persistent or significant disability/incapacity

### Definition of Terms

Life threatening: An AE is life threatening if the subject was at immediate risk of death from the event as it occurred (i.e., it does not include a reaction that if it had occurred in a more serious form might have caused death). For example, drug-induced hepatitis that resolved without evidence of hepatic failure would not be considered life threatening even though drug-induced hepatitis can be fatal.

Hospitalization: AEs requiring hospitalization should be considered SAEs. Hospitalization for elective surgery or routine clinical procedures that are not the result of an AE (e.g., elective surgery for a pre-existing condition that has not worsened) need not be considered AEs or SAEs. If anything untoward is reported during the hospitalization, that occurrence must be reported as an AE, either 'serious' or 'non-serious' according to the usual criteria.

In general, hospitalization signifies that the subject has been detained (usually involving at least an overnight stay) at the hospital or emergency ward for observation and/or treatment that would not have been appropriate in the physician's office or outpatient setting. When in doubt about whether 'hospitalization' occurred or was necessary, the AE should be considered serious.

Disability/incapacity: An AE is incapacitating or disabling if the experience results in a substantial and/or permanent disruption of the subject's ability to perform normal life functions.

### **6.3 Documenting Adverse Events/Serious Adverse Events**

Sites and mobile phlebotomists must observe normal SOC practices to protect the subjects' health and safety during the specimen collection. For SAEs, at each occurrence, the event should be reported to the regulatory body (the Institutional Review Board, IRB) within 1 business day of Investigator knowledge of such event.

## **7. STATISTICS**

If discrepancies exist between the text of the statistical analysis as planned in the protocol and the final statistical analysis plan (SAP), a protocol amendment will not be issued, and the SAP will prevail.

The SAP will be finalized prior to the end of clinical database lock for the study. Any changes to the methods described in the final SAP will be described and justified in the clinical study report.

### **7.1 Evaluable Status**

A subject may be considered unevaluable and therefore excluded from all primary and secondary analyses if any of the following criteria are met: (Note this list is not exhaustive. Refer to the SAP for details.)

- No Freenome test result (for example, resulting from errors in labeling, improper collection or handling, and poor specimen quality)
- Missing any of the required reports, i.e. CS and, if applicable, histopathology and imaging reports
- Incomplete CS, or no photographic evidence or documentation of cecal intubation (unless diagnosed with CRC)
- Bowel preparation quality rated as poor or inadequate (unless diagnosed with CRC)
- Subjects found to have occult IBD on CS

Unevaluable subjects will be assessed for bias as described in the SAP.

## 7.2 Histopathological Definitions

For this study, the index lesion is considered to be the most clinically significant lesion, and the hierarchy of clinical significance (and the categories of histopathological findings) is as follows:

1. CRC, all stages (I-IV)
2. Advanced adenoma (AA), including
  - 2.1 Adenoma with carcinoma in situ or high-grade dysplasia, any size
  - 2.2 Adenoma, villous growth pattern ( $\geq 25\%$ ), any size
  - 2.3 Adenoma  $\geq 1.0$  cm in size
  - 2.4 Serrated lesion,  $\geq 1.0$  cm in size (includes sessile serrated adenoma/polyp (SSA/P) with or without cytological dysplasia and hyperplastic polyps  $\geq 1.0$  cm)
  - 2.5 Traditional serrated adenoma (TSA), any size
3. Non-advanced adenoma (NAA)
  - 3.1  $\geq 5$  adenomas, all  $< 1.0$  cm in size, non-advanced
  - 3.2  $< 5$  adenomas,  $< 1.0$  cm in size, non-advanced
4. Negative (NEG)
  - 4.1 All SSA/P  $< 1.0$  cm and HP  $< 1.0$  cm not in sigmoid or rectum
  - 4.2 HP  $< 1.0$  cm in the sigmoid or rectum
  - 4.3 Negative upon histopathological review
  - 4.4 No findings on colonoscopy, no histopathological review

Subjects will be placed into a category based on the most clinically significant lesion confirmed by histopathology. Subjects with histopathological findings in categories 3.1-3.2 above will be included in the Sp analysis as NAAs and 4.1-4.4 as NEG. Those subjects in the NEG category will include those subjects with a CS showing no findings (and hence no histopathology submitted), non-neoplastic disease, and/or non-adenomatous (e.g., hyperplastic) polyps  $< 1$  cm in diameter.

## 7.3 Study Endpoints and Test Performance Analyses

### 7.3.1 Co-Primary Endpoint Effectiveness Analysis

The co-primary endpoint effectiveness analysis for the blood test Sn for CRC cases ( $Sn_{CRC}$ ) is to demonstrate whether the lower bound of the two-sided confidence interval for the point-estimate

of  $Sn_{CRC}$  meets or exceeds 65%. The co-primary analysis for Freenome's test  $Sn_{CRC}$  will be performed using an exact binomial test to compute the two-sided 95% confidence lower bound for the percentage of all Full Analysis Set (FAS) subjects identified with CRC from the CS and confirmed histopathology with a positive Freenome test result. The FAS set will include those study-eligible subjects who have an evaluable test result, and an evaluable CS result with confirmed histopathology findings.

The co-primary effectiveness analysis for test Sp for NAA and NEG cases ( $Sp_{NAA+NEG}$ ) is to demonstrate whether the lower bound of the two-sided confidence interval for the point-estimate of  $Sp_{NAA+NEG}$  meets or exceeds 85%. The co-primary analysis for Freenome's test Sp for NAA and NEG subjects in the FAS will be performed using an exact binomial test to compute the two-sided 95% confidence lower bound.

Both lower bound conditions must be achieved for the study to be declared a success.

The robustness of significant results from the analysis of the primary endpoint will be assessed by calculating the numbers of subjects whose test results would have to switch from positive to negative and vice versa to obtain a result that was just significant. All enrolled but excluded cases will be assessed for bias in the analyzed population by comparing the baseline demographics for those included versus those excluded. Including the excluded cases with various proportions of imputed results for the missing elements will be used to further demonstrate the level of robustness of the significant result from the FAS set alone.

### 7.3.2 Secondary Endpoints and Analyses

NPV of Freenome's test:

The analysis for Freenome's test NPV for CRC cases ( $NPV_{Non-CRC}$ ) is to determine whether the lower bound of the two-sided CI for the point-estimate of  $NPV_{Non-CRC}$  meets or exceeds the prevalence for Non-CRC in the study population. The analysis for Freenome's test  $NPV_{Non-CRC}$  will be performed using an exact binomial test to compute the two-sided 95% confidence lower bound for the rate among FAS subjects with a test-negative result for those identified without CRC from CS and histopathology.

PPV of Freenome's test:

The analysis for Freenome's test PPV for CRC cases ( $PPV_{CRC}$ ) is to determine whether the lower bound of the two-sided CI for the point-estimate of  $PPV_{CRC}$  meets or exceeds the prevalence of CRC in the study population. The analysis for Freenome's test  $PPV_{CRC}$  will be performed using an exact binomial test to compute the two-sided 95% confidence lower bound for the rate among FAS subjects with a test-positive result for those identified with CRC from CS and histopathology.

Sensitivity of Freenome's test for AA:

The effectiveness analysis for Freenome's test Sn for AA cases ( $Sn_{AA}$ ) is to determine whether the lower bound of the two-sided CI for the point-estimate of  $Sn_{AA}$  meets or exceeds 25%. The analysis for Freenome's test  $Sn_{AA}$  will be performed using an exact binomial test to compute the two-sided 95% confidence lower bound for the percentage of all FAS subjects identified with AA from CS and histopathology with a test-positive result.

### 7.3.3 Sample Size Justification

The study should include a minimum of 48 evaluable adenocarcinoma cases meeting the requirements for inclusion in the analysis set for the co-primary Sn endpoint. Assuming a prevalence of 0.3% CRC cases, the minimum number required in the FAS is approximately  $48/0.3\% = 16,000$  subjects. Allowing for a 30% unevaluable rate, this gives an enrollment of 22,857 subjects. A sample size of 48 CRC achieves 90.4% power to rule out a Sn of 65% using a one-sided exact test with a target significance level of 0.025. The actual significance level achieved by this test is 0.025 (PASS 2019, v19.0.2).

If 48 CRC cases are tested, then at least 38 need to be positive by Freenome's test to rule out a lower bound of 2-sided 95% CI (Clopper-Pearson method) of 65%. The lower bound of 38/48 CI is 65.1%.

### 7.3.4 Additional Analyses

Additional analyses include, for example, analysis of distribution of cancers by age, biological sex, race, and ethnicity: Using a chi square or Fisher's exact test of the observed incidence of CRC (or CRC and AA) relative to the expectation from SEER incidence data will help assess the representativeness of the study population.

Direct rate standardization will be used to project the Sn and Sp (for CRC and AA) of Freenome's test to the general population, males, females and subjects  $\geq 65$  years of age.

The distribution and receiver operating characteristic (ROC) curves for Freenome's test score among the FAS subject group separately will be included. The AUC of each curve will be presented with its estimated 95% CI. For the same groups, the Sn and Sp of subject test scores will be presented over the range of scores, with Youden's J and number needed to misdiagnose one (NNMD) superimposed on the figure.

More details of analyses will be described in the SAP.

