## 3. STUDY DESIGN

### 3.1 Study Overview

This is an international multi-center study for the clinical validation of Freenome's blood test to detect ACN (i.e., CRC and AA). Subjects referred by a healthcare provider (HCP) for a standard of care (SOC) screening CS and providing informed consent are eligible to participate based on the study inclusion and exclusion criteria. Enrollment procedures should be completed within 30 days of signing consent. Should a patient fall outside of the 30-day window, these cases may be escalated to Freenome (or designee) for approval on a case by case basis.

- Subjects who provide informed consent, meet the eligibility criteria and provide the blood sample for this study will be enrolled. Subjects will undergo blood collection and will then have 90 days to complete a SOC screening CS. Maximum time allowed between enrollment and CS will be 90 days. Subjects will have the option to have blood collection done either at the clinical study site or by a study-provided mobile phlebotomy service, in which case the subject can have blood collected in their home or location of preference. Up to 50 mL of blood will be collected from each enrolled subject prior to the bowel preparation for CS. Blood specimens will be used for the clinical and analytical validation of Freenome's test. Blood specimens will be de-identified and sent to Freenome, or a designee, for processing, storage and testing. De-identified specimens and residual specimens will be banked and may be utilized for additional analytical validation testing by Freenome, to improve the current assay in the future, or to develop new assays. Specimens will be used for research purposes only. Since Freenome's test (and any future testing using residual specimens) is currently investigational, results will not be shared with Investigators or subjects.

Study duration is comprised of the time between enrollment and a single study visit for a SOC screening CS and should be no longer than 90 days.

Although no long-term follow-up is planned, subjects may also be contacted by site personnel up to three (3) years following the completion of the study to gather additional information (e.g., any new cancer diagnoses).

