8.5. Additional Analyses

1. Descriptive statistics for medical history, concomitant medication, adverse events, summary of blood test accessioning, processing, and findings, and summary of colonoscopy findings.
2. Diagnostic yield.
3. Report percentage of results with invalid tests.
4. Subject demographics and analysis of test performance (Sn, Sp, PPV, NPV, PLR and NLR) homogeneity by sites stratified by Science 37 and non-Science 37 sites, and US vs non-US sites.
5. Analysis of test performance (Sn, Sp, PPV, NPV, PLR and NLR) for the following age-based USPSTF (2021) Grade groups:
 - 5.1. USPSTF Grade "A" (50-75)
 - 5.2. USPSTF Grade "A+C" (50-85)
 - 5.3. USPSTF Grade "B+A" (45-75)
 - 5.4. USPSTF Grade "B+A+C" (45-85)
6. Comparison of age and sex distributions to US estimates.
7. NPV and PPV using U.S. IUP prevalence.

This document contains confidential, proprietary information and may not be reproduced or disclosed in whole or in part without written authorization from Freenome Holdings, Inc

		Approval Status	Approved
		Effective Date	5-Jan-2024
Document Number	PL-00052	Current Revision	5
Document Title	Clinical Validation of Freenome's Methylation Blood Test for the Early Detection...		
Document Category	Plan		

8. Direct rate standardization will be used to project the sensitivity (Sn_{ACN} , Sn_{CRC} , and Sn_{AA}) and specificity ($Sp_{non-ACN}$) of FMBT-CRC to the general population based on age brackets and biological sex. Standardization will be repeated, projecting for condition prevalence (based on age brackets and sex) to the general population, prior to projecting the sensitivity and specificity to the general population.
9. Number needed to screen per disease-positive finding (CRC, Stage I to III CRC, AA).

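### Protocol 7.3.4 compares a one-time screening prevalence of CRC with SEER incidence and gives no conversion, so a rejection on level would not show that the cohort is unrepresentative

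*Protocol*

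**What the plan says.** Protocol 7.3.4 introduces, as an example of an additional analysis, an "analysis of distribution of cancers by age, biological sex, race, and ethnicity". It then names the method: a chi-square or Fisher's exact "test of the observed incidence of CRC (or CRC and AA) relative to the expectation from SEER incidence data", which "will help assess the representativeness of the study population". It gives no SEER rate, reference period, weighting or decision rule, and refers to the SAP for details.

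Protocol 3.1 describes the observation period as the time between enrollment and "a single study visit for a SOC screening CS and should be no longer than 90 days". On what comes later it says "Although no long-term follow-up is planned", although sites may contact subjects for up to three years. Protocol 7.3.3 treats the CRC yield as a prevalence: "Assuming a prevalence of 0.3% CRC cases".

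SAP Rev 5 section 8.5 does not list the SEER comparison. Item 6 there reads "Comparison of age and sex distributions to US estimates", and item 8 is direct standardisation. Protocol section 7 lets the SAP prevail where the two documents differ. SAP section 4 says that the SAP is to be read together with the protocol.

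**The concern.** Incidence counts new diagnoses per person-year. A single colonoscopy in people due for screening finds cancers that are already present and undiagnosed. In a rough steady state, that prevalence equals annual incidence multiplied by the mean number of years a cancer is detectable before it would be diagnosed. The two levels agree only if that time is about one year. Otherwise they differ even in a perfectly representative cohort, and the test reports the difference as if it bore on who was enrolled.

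The variant that adds AA is further off. The documents cite SEER only for cancer, so there is no AA expectation for the AA findings to be compared with.

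At stake is the interpretation of a supportive claim, that the cohort represents the intended use population. SAP section 4 itself uses both prevalence and incidence for the study's CRC rate, so the benchmark needs to be named clearly.

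**Working it through.** **Inputs from the documents**

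- CRC yield 0.30% (protocol 7.3.3; SAP section 7).
- Analysis-set size: 16,000 (protocol 7.3.3) and 19,000 (SAP section 7).
- Significance level 0.05 for tests outside the primary and secondary endpoints (SAP 8.2), taken as two-sided.
- Prevalence distributions in SAP section 7: CRC Beta(3.264, 816.77), AA Beta(34.265, 436.699).

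**Input that is assumed:** the annual SEER rate that applies to the enrolled ages, varied from 0.05% to 0.30%.

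**Step 1: the plan's own sizes.** 48/0.003 = 16,000, as the protocol states, and 16,000/0.70 = 22,857. The SAP's 56/0.003 = 18,667 is rounded to 19,000. Neither document gives an error rate for the SEER comparison, so there is none to reproduce.

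**Step 2: level comparison.** With N subjects and annual rate r, the expected count is N × r. A two-sided exact binomial test rejects outside limits c_lo and c_hi, each with tail probability at most 0.025 under r. For a representative cohort the observed count X is Binomial(N, 0.003), so P(reject) = P(X ≤ c_lo) + P(X ≥ c_hi). The mean of X is 48 at N = 16,000 and 57 at N = 19,000.

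| Assumed annual rate | Expected, N = 16,000 | P(reject) | Expected, N = 19,000 | P(reject) |
|---|---|---|---|---|
| 0.05% | 8.0 | 100% | 9.5 | 100% |
| 0.10% | 16.0 | 100% | 19.0 | 100% |
| 0.15% | 24.0 | 97.9% | 28.5 | 99.3% |
| 0.20% | 32.0 | 68.7% | 38.0 | 76.4% |
| 0.25% | 40.0 | 21.1% | 47.5 | 27.1% |
| 0.30% | 48.0 | 4.3% | 57.0 | 4.6% |

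The last row is the check: when the expectation matches the prevalence, the test holds its level. A chi-square test against a fixed rate is similar (98.6%, 73.8% and 25.4% at 0.15%, 0.20% and 0.25%, N = 16,000). At N = 16,000, rejection reaches 95% only for rates up to about 0.162%, a prevalence-to-incidence ratio of 0.300/0.162 = 1.85.

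All these figures treat the SEER expectation as known without error. If it were entered as a second sample of 16,000, rejection at 0.15% would be roughly 81%.

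**Step 3: sensitivity to the yield.** The SAP's mean CRC prevalence is 3.264/(3.264 + 816.77) = 0.398%. At that yield, rejection at 0.20% is 99.4% (N = 16,000) and 99.8% (N = 19,000). At 0.25% it is 90% and 95%. The 0.30% used above gives the smaller effect.

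**Step 4: CRC and AA together.** The SAP's mean AA prevalence is 34.265/(34.265 + 436.699) = 7.28%. The combined yield is 0.398% + 7.28% ≈ 7.7%, or about 16,000 × 0.077 ≈ 1,230 subjects. A cancer rate of 0.25% would predict 40. Rejection is practically certain.

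**Step 5: distribution across strata.** Suppose instead that only the split of cancers across strata is tested, with the expectation in each stratum proportional to (enrolled number × SEER rate), and that prevalence is proportional to incidence. Simulation with illustrative strata gave a rejection rate of about 5.2% for 48 cases. With 70% of subjects aged 65 or over it was 5.3% for 48 cases and 5.2% for 57. The test then keeps its nominal level, but only under those two conditions.

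**The case against.** Four points count against a stronger claim.

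- **The SAP governs.** It lists its additional analyses without this test and compares age and sex with US estimates instead. On that view the protocol sentence, offered only as an example, is inoperative. This stands in part. The SAP does not carry the test, but it also does not withdraw it, and it asks to be read with the protocol. A reader cannot tell whether the test will be run.
- **The lead-in speaks of distribution.** On that reading the test can work, as Step 5 shows. This stands, with the limit that neither weighting to enrolled numbers nor proportionality is stated, and that the quantity named for testing is an incidence against an expected incidence.
- **The SEER rate is unknown.** A reader might infer that a representative cohort would fail almost every time. The documents do not support that without a rate. It holds up to roughly 0.16% per year at a 0.30% yield, and no longer holds at 0.25%. The target of at least 70% aged 65-85 would move the applicable rate upward if incidence rises with age, which weakens the effect.
- **Nothing is declared.** The test only helps to assess representativeness. It has no decision rule and no part in the success criteria.

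A reader might also infer that the age target makes any comparison of distributions fail by design. That follows only if raw case shares are set against national shares. An expectation built from stratum rates and enrolled numbers already absorbs the enrichment.

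**Conclusion.** The defect is real and limited. As a comparison of levels, protocol 7.3.4 sets a prevalence against an incidence, so a rejection cannot be taken as evidence of non-representativeness. The false-alarm rate in a representative cohort is about 98-100%, 69-76% or 21-27% at assumed SEER rates of 0.05-0.15%, 0.20% or 0.25%, given a true yield of 0.30%, 16,000 to 19,000 subjects and a fixed expectation. Adding AA makes rejection nearly certain. The distribution reading is roughly valid under conditions that the protocol leaves unstated.

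The primary and secondary conclusions are untouched. It would also go too far to infer that the SAP's April 5, 2021 enrollment cut-off rests on this test. The SAP argues for that date from pandemic effects on participation and from sample storage time. It mentions the CRC rate as support but cites no SEER test.

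**What to change.** Change the SAP only; no protocol amendment is needed, because the SAP prevails.

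1. State in SAP 8.5 that the SEER incidence-level test in protocol 7.3.4 is replaced.
2. Extend item 6 from age and sex to race and ethnicity.
3. Report age- and sex-standardised CRC and AA detection with 95% confidence intervals beside screening-colonoscopy prevalence, and show the uncertainty of that benchmark. If the SAP's own CRC beta distribution is used, give its 95% range of about 0.09% to 0.93% along with the mean of 0.398%. A benchmark that wide can detect only gross departures.
4. If SEER is kept, limit it to the distribution of CRC across strata, weight the expectations to the enrolled numbers per stratum, state the proportionality assumption, and leave AA out.

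The cost is a few sentences and one table from data already collected.
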